1. SCHEMA

[figure not shown]

Figure 1: Treatment schema and correlative endpoints that will determine a) whether CTC analysis can contribute to an assessment of PTPN12 status and response to treatment b) whether acute changes in ddPCR assessment of ctDNA can predict the outcome of subsequent response determined radiologically and c) conduct proteogenomic analysis of snap frozen OCT-embedded tumor biopsies to analyze the TNBC kinome and perturbations induced by treatment with sitravatinib.

2. STUDY DESIGN/SUMMARY

This is a phase II, two cohort trial designed to evaluate the efficacy of sitravatinib in patients with metastatic triple-negative breast cancer (mTNBC) after treatment with at least one line of chemotherapy for advanced disease. The drug, sitravatinib at 100 mg, will be dosed daily at the initiation of the study and continued until progression or unacceptable toxicity.

The study will employ a modified optimal Simon's two stage design. Participants will be recruited into two cohorts: Protein Tyrosine Phosphatase, Non-Receptor Type 12 (PTPN12) low or PTPN12 high/normal cohorts simultaneously and independently. Seven participants will be enrolled to each arm during the first stage. After the first stage, depending on the observed number of responses, the study will proceed to the second stage utilizing an adaptation of the Jones and Holmgren approach [1]. The primary endpoint is progression-free survival status at 24 weeks (PFS24) and the secondary endpoints will include: Time to Progression (TTP), Objective Response Rate (ORR), Clinical Benefit Rate (CBR), and grade 3 or higher adverse events. The maximum accrual needed is 25 participants. This study approach will have 90% power to detect PFS24 rate of 30% in the PTPN12*low* stratum, or 85% power to detect a PFS24 rate of 25% in the unselected population.

3. OBJECTIVES

3.1 Primary Objective

To evaluate the efficacy of sitravatinib as measured by progression-free survival at 24 weeks (PFS24), as evaluated by RECIST version 1.1, in participants with mTNBC that have been treated with at least one line of chemotherapy.

3.2 Secondary Objectives

- 3.2.1 To evaluate Time to Progression (TTP), defined as the duration of time from initiation of treatment until progression according to RECIST 1.1 criteria
- 3.2.2 To evaluate Objective Response Rate (ORR), defined as the proportion of participants who achieve a Complete Response (CR) or Partial Response (PR) to treatment per RECIST 1.1 criteria
- 3.2.3 To evaluate the Clinical Benefit Rate (CBR), defined as the proportion of participants who achieve CR, PR, or stable disease (SD) per RECIST 1.1 criteria
- 3.2.4 To evaluate the number of participants with grade 3 or higher adverse events as per the NCI Common Terminology Criteria for Adverse Events version 5.0 (CTCAEv5)

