5. PARTICIPANT SELECTION

5.1 Inclusion Criteria

- 5.1.1 Women or men age 18 and older
- 5.1.2 Metastatic or locally advanced inoperable breast cancer (beyond curative management) that is measureable according to RECIST 1.1 criteria.
NOTE: Patients with bone-only disease are eligible if there is at least one lytic lesion that can be followed for response.
- 5.1.3 Tumor is ER-negative and PR-negative per ASCO/CAP Guidelines of 2010
- 5.1.4 Tumor is HER2neu-negative per ASCO/CAP Guidelines of 2018
- 5.1.5 Patient has archival tissue from metastatic or locally advanced breast cancer for the analysis of PTPN12 status.
NOTE: For patients who do not have archival tissue available, a research biopsy of the locally advanced or metastatic breast tumor is required.
- 5.1.6 At least one prior line of chemotherapy with or without a PD-L1 or PD-1 antibody in the metastatic setting
- 5.1.7 ECOG performance status ≤ 2 (Karnofsky $\geq 60\%$)
- 5.1.8 Normal organ and hematologic function as defined below:

 Absolute neutrophil count Hemoglobin Platelets Total bilirubin AST (SGOT)/ALT (SGPT)	$> 1000/\text{mcL}$

 Creatinine Creatinine clearance Normal LVEF function defined as normal LV wall motion and ejection fraction of $\geq 50\%$	$> 11 \text{ g/dL}$
	$\geq 100,000/\text{mcL}$
	$\leq 1.5 \times \text{normal institutional limits}$
	$\leq 2.5 \times \text{institutional ULN or } \leq 5.0 \times \text{ULN for patients with documented liver metastases.}$
	within normal institutional limits
	$\geq 30 \text{ mL/min}$
- 5.1.9 If patient has brain metastasis, documented treatment and stability for at least 30 days by scans and off steroids at the time of enrollment
- 5.1.10 Women of child-bearing potential and actively menstruating must have a negative pregnancy test prior to starting study treatment
- 5.1.11 If sexually active in a way that could lead to pregnancy, participant must agree to use a highly effective method of birth control starting at the time of informed consent and continuing throughout the study and for at least 3 months after the final dose of sitravatinib. Highly effective methods of birth control include:
 - Intrauterine device
 - Condoms with spermicide
 - Bilateral tubal occlusion/ligation

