12.1.2 Evaluable for Objective Response

Only those participants who have measurable disease present at baseline, have received at least one cycle of study treatment, and have had their disease re-evaluated, will be considered evaluable for response. These participants will have their response classified according to the definitions outlined in Section 12.4. (Note: Participants who exhibit objective disease progression prior to the end of Cycle 1 will also be considered evaluable.)

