12.1.5 Non-Measurable Disease

All other lesions (or sites of disease), including small lesions (longest diameter < 10 mm or pathological lymph nodes ≥ 10 to < 15 mm), are considered non-measurable disease. Bone

lesions, leptomeningeal disease, ascites, pleural/pericardial effusions, lymphangitis cutis/pulmonitis, inflammatory breast disease, and abdominal masses (not followed by CT or MRI), are considered non-measurable.

NOTE: Cystic lesions that meet the criteria for radiographically defined simple cysts should not be considered as malignant lesions (neither measurable nor non-measurable) since they are, by definition, simple cysts. Cystic lesions thought to represent cystic metastases can be considered as measurable lesions, if they meet the definition of measurability described above. However, if non-cystic lesions are present in the same participant, these are preferred for selection as target lesions. In addition, lymph nodes that have a short axis < 10 mm are considered non-pathological (i.e., normal) and should not be recorded or followed.

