12.4.5 Evaluation of Best Overall Response

The best overall response is the best response recorded from the start of study treatment until disease progression/recurrence (taking as reference for progressive disease the smallest measurements recorded since the treatment started). The participant's best response assignment will depend on the achievement of both measurement and confirmation criteria.

For participants with measurable disease at baseline:

Target Lesions	Non-Target Lesions	New Lesions	Overall Response
CR	CR	No	CR
CR	Non-CR/ Non-PD	No	PR
CR	Not evaluated	No	PR
PR	Non-PD or not all evaluated	No	PR
SD	Non-PD or not all evaluated	No	SD
Not all evaluated	Non-PD	No	Non-evaluable
PD	Any	Yes or No	PD
Any	PD*	Yes or No	PD
Any	Any	Yes	PD

*In exceptional circumstances, unequivocal progression in non-target lesions may be accepted as disease progression.

For participants with non-measurable/evaluable disease only at baseline:

Non-Target Lesions	New Lesions	Overall Response
CR	No	CR
Non-CR/Non-PD	No	Non-CR/Non-PD
UNK/Not All Evaluated	No	Indeterminate
Unequivocal progression	Yes or No	PD
Any	Yes	PD

In some circumstances, it may be difficult to distinguish residual disease from normal tissue. When the evaluation of complete response depends on this determination, it is recommended that the residual lesion be investigated (fine needle aspirate/biopsy) to confirm the complete response status.

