16. STATISTICAL CONSIDERATIONS

16.1 Study Design

This phase 2 biomarker-stratified study employs a modified optimal Simon two stage design. The decision rule, based on an adaptation of the approach of Jones and Holgren[1], is detailed below.

The primary endpoint is PFS24, where the success is defined as being alive and progression-free at 24 weeks after initiation of study treatment.

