16.6 Reporting and Exclusions

All PFS-evaluable participants will be included in analyses of the primary and secondary outcomes in their assigned group (modified-ITT population). All participants who receive any study treatment will be considered evaluable for the safety analysis (safety population).

All registered participants will be accounted for. Participants withdrawn or considered ineligible before starting study treatment will be replaced. Participants withdrawn prior to completing the first cycle of study treatment or determined to be ineligible, will be considered inevaluable for PFS24 and will be replaced.

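### The clinical benefit rate omits Non-CR/Non-PD, so bone-only participants with controlled disease short of CR can never count as benefiting

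*Combined protocol and SAP*

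**What the plan says.** - **Eligibility (5.1.2).** Measurable disease is required, with one exception: "Patients with bone-only disease are eligible if there is at least one lytic lesion that can be followed for response".
- **Measurability (12.1.5).** The list of non-measurable sites opens with bone "lesions, leptomeningeal disease, ascites, pleural/pericardial effusions, lymphangitis cutis/pulmonitis, inflammatory breast disease". Lytic lesions are not excepted.
- **Response categories (12.4.5).** There is a separate table headed "For participants with non-measurable/evaluable disease only at baseline". Its possible overall responses are CR, Non-CR/Non-PD, Indeterminate and PD.
- **Stable disease (12.4.2.4).** SD is defined through the sum of target-lesion diameters. Non-CR/Non-PD is defined separately, for non-target disease, in 12.4.3.2.
- **CBR (3.2.3).** It is "defined as the proportion of participants who achieve CR, PR, or stable disease (SD) per RECIST 1.1 criteria". No other category is named.
- **Evaluability (12.1.3).** Participants with evaluable but non-measurable disease form their own class, evaluable for non-target response. The section does not mention CBR.
- **Primary endpoint (16.1).** For PFS24, "the success is defined as being alive and progression-free at 24 weeks after initiation of study treatment". Measurable disease is not needed.
- **Analysis set (16.6).** "All PFS-evaluable participants will be included in analyses of the primary and secondary outcomes in their assigned group". This is the modified-ITT population.
- **Analysis (16.5.2).** CBR is summarized descriptively.

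**The concern.** The protocol lets in a small group on purpose and then scores CBR with categories that this group cannot reach. With measurable disease, a participant who neither responds nor progresses is SD and counts as clinical benefit. With bone-only disease, the same course is Non-CR/Non-PD and does not count. The difference comes from how the lesion is measured and not from how the patient did.

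At stake is the interpretation of one secondary endpoint. CBR would be understated whenever such participants are enrolled. The report could show a participant as a success on the primary endpoint and as having had no clinical benefit, with nothing in the plan to explain it. An analyst who noticed the gap would have to settle it after seeing the data.

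**Working it through.** **The plan's own figures.** The plan states no expected CBR. Its only computed design figures are the PFS24 powers in 16.3, which the 16.2 rules reproduce:

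- PTPN12 low path (at least 1 of 7, then at least 2 of 15) at a rate of 30%: 1 − 0.7^7 − [7 × 0.3 × 0.7^6] × 0.7^8 = 1 − 0.0824 − 0.0142 = 0.903. Stated: 90%.
- Unselected path (at least 1 of 7 high/normal, then at least 3 of 25) at 25%: the sum over h = 1 to 7 of P(h of 7) × P(at least 3 − h of the other 18) = 0.852. Stated: 85%.

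Neither calculation uses a response category, so the CBR definition cannot affect them.

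**Tracing one participant.** Take bone-only disease that persists without progression through 24 weeks.

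| Step | Section | Result |
|---|---|---|
| Eligible? | 5.1.2 | Yes, by the exception |
| Measurable? | 12.1.5 | No |
| Best overall response | 12.4.5, non-measurable table | Non-CR/Non-PD |
| Could it be SD? | 12.4.2.4 | No; there is no target-lesion sum |
| PFS24 | 16.1 | Success |
| In the secondary analysis set? | 16.6 | Yes |
| In the CBR numerator? | 3.2.3 | No |

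**Size per participant.** In the 16.6 set each such participant lowers CBR by 1/n, compared with a rule that counts Non-CR/Non-PD:

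- n = 25 (unselected path): 1/25 = 4.0 points
- n = 15 (PTPN12 low path): 1/15 = 6.7 points
- n = 7 (a cohort that closes after Stage 1): 1/7 = 14.3 points

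The last figure needs care. Under 16.2 a cohort closes at 7 only if it had no PFS24 success. There, the 14.3 points can come only from a participant who was Non-CR/Non-PD and later failed PFS24, so the figure cannot illustrate a conflict between the two endpoints.

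**Illustration.** The documents give no number of bone-only participants, so the counts here are assumptions: n = 25, 8 participants with CR, PR or SD, and b further bone-only participants with Non-CR/Non-PD. Limits are exact (Clopper-Pearson) and not adjusted for the two stages.

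| b | CBR as written, 8/25 | CBR counting Non-CR/Non-PD, (8 + b)/25 |
|---|---|---|
| 0 | 32% (15–53%) | 32% (15–53%) |
| 1 | 32% (15–53%) | 36% (18–57%) |
| 2 | 32% (15–53%) | 40% (21–61%) |
| 3 | 32% (15–53%) | 44% (24–65%) |

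The differences, 4 to 12 points for b = 1 to 3, lie well inside the intervals.

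**The case against.** The strongest reply is that nobody would be misled. The eligibility note speaks of following the lytic lesion for response, so the authors may have meant to treat it like a target lesion, or to read Non-CR/Non-PD as the equivalent of SD. Section 12.1.3 shows that these participants were not forgotten. But 12.1.5 makes no exception for lytic lesions, the protocol defines SD and Non-CR/Non-PD separately, and 12.1.3 is not linked to CBR. If that was the intention, the text still has to say so.

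A second reply is that CBR and PFS24 need not agree. Section 3.2.3 sets no minimum duration for SD, so a participant with one early SD scan can count for CBR and fail PFS24. That is correct, and disagreement alone is not the defect. The defect is that equal disease control is scored differently according to measurability.

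Third, the group may be empty. That stands, and it limits the size of the point.

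A reader might go further and infer two things that the documents do not support.

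- **That 12.1.2 and 16.6 give conflicting denominators for ORR and CBR.** Section 12.1.2 does say "Only those participants who have measurable disease present at baseline, have received at least one cycle of study treatment", together with re-evaluation, are evaluable for response. It goes on to say how their response is classified, so it is naturally read as settling who receives a response category. Section 16.6 settles who is in the secondary analyses. Even if 12.1.2 were used, the bone-only participant would leave the denominator and would still not enter the numerator.
- **That the replacement rule in 16.6 removes participants who progress or die in Cycle 1.** Section 7.2.2 lists progression and death as reasons to discontinue treatment, and 7.2.3 ties withdrawal to consent. The note in 12.1.2 also points towards keeping progressors: "Participants who exhibit objective disease progression prior to the end of Cycle 1 will also be considered evaluable". The looser use of withdrawal in the proteinuria guidance (9.1.10) is too little to overturn that reading.

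**Conclusion.** The point holds, as a minor one. As written, 3.2.3 shuts bone-only participants with controlled disease short of CR out of the CBR numerator, although 16.1 can count the same participants as PFS24 successes. Each one costs 4.0 points of CBR at n = 25 or 6.7 points at n = 15. These figures assume the 16.6 set as denominator and 12.1.5 applied as written to lytic bone lesions. The total effect depends on a count that the documents do not give, and it is zero if no such participant is enrolled.

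It would be wrong to infer that the primary result is at risk. The PFS24 definition, its thresholds (3 of 25, 2 of 15) and the stated power do not depend on CBR.

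**What to change.** In 3.2.3, state that for participants with non-measurable disease only (the 12.1.3 class), a best overall response of Non-CR/Non-PD counts as clinical benefit alongside SD. State that Indeterminate counts as no benefit and that the 16.6 modified-ITT set remains the CBR denominator.

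The cost is a few words and no new data, since 12.4.5 already assigns the category. The drawback is that Non-CR/Non-PD is coarser than SD: it rests on lesions persisting without unequivocal worsening and not on a measured sum. Like SD in 3.2.3, it carries no minimum duration, so a single early non-progressing assessment would count. To let readers judge this, 16.5.2 may add CBR in participants with measurable disease alone as a labelled supplement.

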7.2 Treatment Phase

Once registered/enrolled, participants will start treatment with sitravatinib 100 mg once daily until disease progression (assessed by RECIST 1.1), unacceptable toxicity, death or discontinuation from treatment for any other reason. Each cycle is 28 days in length. Study assessments, and efficacy and safety monitoring will continue as outlined in the study calendar.

All assessments must be performed prior to the administration of study treatment unless otherwise specified. The following windows apply:

- On-study assessments for all cycles must be performed within +/- 3 days of Day 1, unless otherwise indicated.
- Re-staging scans for tumor evaluations should continue on schedule if treatment is held or delayed.

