8. STUDY CALENDAR

Test/Procedure	Pre-Study ¹	C1D1	C1D14	Subsequent Cycles Day 1	End of Treatment	Safety Follow-Up ¹¹	Survival Follow-Up
Informed Consent	X						
Participant Demographics	X						
CLINICAL EVALUATIONS							
History and Physical Exam	X	X	X	X	X		
Height	X						
Vital signs and weight	X	X	X	X	X		
Performance Status	X	X	X	X	X		
LABORATORY/RADIOLOGIC EVALUATIONS							
CBC/differential	X		X	X	X		
Comprehensive Metabolic Panel	X		X	X	X		
TSH	X		X	^{X⁴} (odd cycles)	X		
Urine Protein/Creatinine Ratio	X		X	^{X⁴} (odd cycles)	X		
Pregnancy test	^{X²}						
Tumor Assessments	X			^{X⁵}	X		
Echocardiogram	X			^{X⁶}			
TREATMENT DISPENSATION							
Sitravatinib		X		X			
CORRELATIVE							
ctDNA collection	X		X	^{X⁷}	X		
CTC collection	X		X	^{X⁷}	X		
Tumor/Tissue Biopsy ⁸	^{X¹⁰}		^{X³}		X		
Archival tissue	^{X⁹}						
ADDITIONAL INFORMATION							
Concomitant Medications	X		X	X	X	X	
Adverse Events/Toxicity Assessment				X	X	X	
Compliance Assessment				X	X		
Assess vital status							^{X¹²}

NOTE: The schedule may be modified +/- 3 days due to scheduling delays or conflicts (e.g. holidays, inclement weather, vacations, etc.)

1. All pre-study assessments, with the exception of the informed consent, must be performed within 28 days prior to starting study treatment, unless otherwise indicated.
2. Urine or serum pregnancy test is acceptable; to be performed for women of child-bearing potential only
3. May be performed any time between Cycle 1, Day 14 and Cycle 3, Day 14
4. To be performed prior to dosing on C3D1, then prior to dosing on Day 1 of every odd-numbered cycle thereafter (e.g., C5D1, C7D1, etc.)
5. Clinical and radiological tumor assessments will be performed by CT, PET or MRI scan at baseline and then every 2 cycles (i.e., within 7 days prior to Cycles 3, 5, 7, and 9) until disease progression. The same testing modality should be used for each evaluation. Responses of CR or PR should be confirmed with a second assessment no earlier than 4 weeks, but no later than the next scheduled scan, per protocol. Brain MRI and bone scan should be performed if clinically indicated (e.g., participants with known history of bone or brain mets). Results must be reviewed for each scan prior to dosing at next cycle
6. To be performed within 7 days prior to C4D1. Further echocardiograms may be performed as clinically indicated.
7. To be collected on C2D1, C3D1, then on Day 1 of each odd-numbered cycle thereafter (e.g., C5D1, C7D1, etc.)

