12.4.2.4 Stable Disease (SD)

Neither sufficient shrinkage to qualify for PR nor sufficient increase to qualify for PD, taking as reference the smallest sum diameters while on study.

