12.4.8 Confirmatory Measurement/Duration of Response

12.4.8.1 Confirmation of Response

To be assigned a status of PR or CR, changes in tumor measurements must be confirmed by repeat assessments performed no less than 4 weeks after the criteria for response are first met.

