12.4.8.3 Duration of Stable Disease

The duration of SD is measured from the start of the treatment until the criteria for progression are met, taking as reference the smallest measurements recorded since the treatment started, including the baseline measurements.

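### Clinical benefit rate counts stable disease of any duration, so one non-progressing scan at about week 7 to 8 is enough in a trial that judges efficacy at 24 weeks

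*Combined protocol and SAP*

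**What the plan says.** Section 3.2.3 defines CBR as "defined as the proportion of participants who achieve CR, PR, or stable disease (SD) per RECIST 1.1 criteria". Five other places could have added a time requirement, and none does:

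- Section 12.4.2.4 defines stable disease by size change alone: "Neither sufficient shrinkage to qualify for PR nor sufficient increase to qualify for PD".
- Section 12.4.5 states: "The best overall response is the best response recorded from the start of study treatment until disease progression/recurrence". One stable reading before progression is enough.
- Section 12.4.8.1 asks for confirmation of responses only: "To be assigned a status of PR or CR, changes in tumor measurements must be confirmed by repeat assessments". The repeat comes at least 4 weeks later. Stable disease has no counterpart.
- Section 12.4.8.3 says how to measure the length of stable disease ("The duration of SD is measured from the start of the treatment until the criteria for progression are met"), but sets no minimum and is not linked to CBR.
- Section 16.5.2 summarises CBR descriptively and adds no condition.

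On timing, section 7.2 states "Each cycle is 28 days in length", and footnote 5 of the study calendar (section 8) places scans at baseline and "then every 2 cycles (i.e., within 7 days prior to Cycles 3, 5, 7, and 9) until disease progression". Section 16.1 defines primary success as being alive without progression at 24 weeks, and section 16.3 names 3% as the unacceptable rate.

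**The concern.** The name of the endpoint promises more than its rule requires. A response must hold for at least 4 weeks before it counts, but stable disease counts on a single reading. The earliest scheduled reading comes about a third of the way to the time point at which the trial itself judges the drug. A participant stable before Cycle 3 who progresses on the scan before Cycle 5 is a failure for PFS24 and a success for CBR.

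The stake is interpretation. The trial has no control arm and the plan states no reference value for CBR. A report could place a moderate clinical benefit rate beside a failed PFS24 result, and the reader could not tell how much of it was short-lived stability.

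**Working it through.** **1. The plan's own figures.** The documents state no expected or null CBR. The figures that can be checked are the PFS24 powers in section 16.3, using the rules in section 16.2.

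- PTPN12-low route (7 then 15 participants, continue with at least 1 success, final success with at least 2): exact binomial power at 30% is 0.903, against 90% stated.
- Unselected route (7 + 7 then 25, continue with at least 1 success in the high/normal cohort, final success with at least 3): power at 25% is 0.852, against 85% stated.

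Both reproduce, so 3%, 25% and 30% are taken as the trial's own null and target PFS24 rates.

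**2. When stable disease can first be recorded.** Cycle 3 Day 1 is day 2 × 28 + 1 = 57. A scan in the 7 days before it falls on days 50 to 56, about week 7 to 8. The next scan, before Cycle 5, falls at about week 15 to 16. The pre-Cycle 7 scan precedes day 6 × 28 + 1 = 169, so it falls on days 162 to 168, about week 23 to 24.

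**3. What the rule scores at a PFS24 of 3%.** Treat any-duration CBR as roughly the probability S(8) of being progression-free at the first scan. The documents give no shape for the PFS curve, so one must be assumed.

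Constant hazard: S(t) = S(24)^(t/24), hence S(8) = S(24)^(1/3).

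| PFS24 | S(8) |
|---|---|
| 3% | 0.03^(1/3) = 31.1% |
| 25% | 0.25^(1/3) = 63.0% |
| 30% | 0.30^(1/3) = 66.9% |

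Sensitivity at a PFS24 of 3%, Weibull: S(8) = 0.03^((8/24)^k).

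| Shape k | S(8) | Ratio to 3% |
|---|---|---|
| 0.5 | 13.2% | 4.4 |
| 0.75 | 21.5% | 7.2 |
| 1 (constant hazard) | 31.1% | 10.4 |
| 1.25 | 41.1% | 13.7 |
| 1.5 | 50.9% | 17.0 |
| 2 | 67.7% | 22.6 |

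With the first scan at week 7, the range over the same shapes is 15% to 74%, and 36.0% under constant hazard.

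**4. In participants.** With 25 participants and constant hazard, 25 × 0.311 = 7.8 would be expected to meet CBR as written, against 25 × 0.03 = 0.75 expected PFS24 successes. Over the Weibull range the first figure runs from 25 × 0.132 = 3.3 to 25 × 0.677 = 16.9. The share of those progression-free at week 8 who fail by week 24 is (0.311 − 0.030)/0.311 = 90% under constant hazard, and 77% (k = 0.5) to 96% (k = 2) over the range.

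**5. Effect of a minimum duration.** Under constant hazard at a PFS24 of 3%, requiring stability to week 16 leaves 0.03^(16/24) = 9.7%. Requiring it to week 24 leaves 3.0%, plus any confirmed responders who progress before then.

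**6. Limits of the approximation.** CBR is not exactly S(8). Section 5.1.2 admits bone-only disease, section 12.1.5 classes bone lesions as non-measurable, and section 12.4.5 gives participants with only such disease the category Non-CR/Non-PD, not SD. Read literally, they can be progression-free and still not count in CBR. Section 16.6 replaces participants withdrawn in Cycle 1, and section 12.4.4 counts symptomatic deterioration as progression. The observed rate could move either way.

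**The case against.** The strongest reply is that little depends on CBR. It is a secondary endpoint without a threshold (16.5.2), and sections 16.2 and 16.5.1 base every decision on PFS24. It will be reported beside PFS24 with its confidence interval, ORR and a Kaplan-Meier curve for time to progression, which would show early progression after one stable scan. The missing control arm affects all the efficacy endpoints alike. This stands. It limits the harm to interpretation but does not supply the missing duration.

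A reader might infer that any-duration CBR cannot distinguish an active drug from an inactive one. The calculation does not support that. Under constant hazard it is 31% at the null against 63% to 67% at the targets. With 25 participants, a cutoff of 12 or more would be reached with probability 0.057 at 31.1% and 0.959 at 63.0%. With 15, a cutoff of 8 or more gives 0.061 at 31.1% and 0.916 at 66.9%. The endpoint carries information, but reading it needs a reference value that the plan does not give.

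A reader might also infer that many of these patients would be stable at week 8 without any drug effect. The documents give no such rate. The 3% is an unacceptable rate, not an untreated one, and section 4.1.1 says only that the disease is aggressive and prognosis after relapse is extremely poor.

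Finally, no document requires 24 weeks as the minimum, and that choice brings CBR close to the primary endpoint. This also stands. The need is for a stated minimum or a more exact label; matching the primary time point is one reasonable choice.

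**Conclusion.** The point holds as a defect of definition. Following the plan as written, one stable scan at about week 7 to 8 is clinical benefit, even if the next scan shows progression.

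Its size rests on an assumed PFS shape. At a true PFS24 of 3%, about 31% would be progression-free at week 8 under constant hazard, and 13% to 68% for Weibull shapes 0.5 to 2. It would be tempting to quote 31%, or ten times PFS24, as a fact about this trial; the documents do not support a single figure. The direction is firm across the range examined, since the lowest value is still more than four times 3%.

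No decision rule, power or type I error is affected. The change is worth making before results are reported, because CBR could look favourable in a trial whose primary endpoint fails.

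**What to change.** In sections 3.2.3 and 16.5.2:

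- Define CBR as confirmed CR or PR, or SD maintained through the pre-Cycle 7 assessment, counting a scan anywhere in its 7-day window. A literal minimum of 24 weeks would exclude participants scanned a few days early.
- State that Non-CR/Non-PD maintained through the same assessment counts for participants with non-measurable disease only.
- If the any-duration version is kept, report it separately under the label disease control rate.

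The cost is a short change of wording in two sections. No scan is added, because the calendar already lists the assessment "within 7 days prior to Cycles 3, 5, 7, and 9". The downside is a lower reported CBR that overlaps more with PFS24; it would differ mainly by the confirmed responders who progress before week 24. A 16-week minimum would overlap less, at 9.7% for a PFS24 of 3% under constant hazard. Whichever minimum is chosen should be written down before the data are analysed.
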